PROTOCOL SHORT TITLE: Choose to Change – Reducing Tobacco Disparities

Protocol Title: **Reducing Tobacco Use Disparities Among Adults in Safety Net Community Health Centers**

Principal Investigators: [name]. (Lead PI)
Northwestern University
[contact]
[contact]

[name]. (Co-PI)
University of Illinois at Chicago
[contact]

[name]. (Co-PI)
Northeastern Illinois University
[contact]

[name]. (Site PI)
Near North Health Services Corporation
[contact]

[name]. (Site PI)
Alliance of Chicago

Biostatistician: [name].
Brown University
[contact]

Version Date: May 14, 2018

ClinicalTrials.gov
Registration Number: NCT03077737

PURPOSE OF STUDY & OBJECTIVES

An estimated 26 million smokers still receive no treatment for their smoking during their primary care visits. Given the persistent clinical system, provider, and patient barriers to addressing smoking, especially among poor populations, an EHR-automated population health management approach that links a healthcare system with community services both clinically and electronically to engage all smokers may increase access to effective treatment. Increased access is especially significant for low-income smokers who are underserved and carry a disproportionate burden of tobacco-related disease. This 2-group randomized controlled trial will evaluate the effectiveness of a person-centered population health management intervention for smoking cessation in low-income smokers. The following aims and hypotheses will be tested:

Primary Aim 1 (Effect on Treatment Engagement): Compare Choose to Change versus Usual Care for engaging low-income smokers in treatment. Hypothesis: Choose to Change will increase the proportion of smokers who complete a behavior counseling call by 6 weeks (24%), compared with Usual Care (10%).

Primary Aim 2 (Effect on Treatment Utilization): Compare Choose to Change versus Usual Care for increasing treatment utilization. Hypothesis: Choose to Change will increase the proportion of smokers who complete ≥ 1 additional behavior counseling calls by 14 weeks (15%), compared with Usual Care (7%).

Primary Aim 3 (Effect on Smoking Cessation): Compare Choose to Change versus Usual Care for increasing smoking cessation. Hypothesis: Choose to Change will increase the proportion of smokers

PROTOCOL SHORT TITLE: Choose to Change – Reducing Tobacco Disparities

abstinent at 28 weeks (7%), as defined by bio-verified 7-day point-prevalence abstinence, compared with Usual Care (2%).

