CtC participants will be mailed the letter on behalf of their provider encouraging cessation or smoking reduction as an initial step to cessation if not ready to set a quit date, provides information about Quitline services, including safety and effectiveness, and states that a Quitline coach will be calling within two weeks to offer free treatment. The central message developed through our previous focus group work is "**Choose to change and make your own goals.**" The letter also contains the other elements of SDT as well as standard evidence-based supportive and motivational statements. Participants who do not want to be called by the Quitline will be instructed to contact the NNHSC study care coordinator. Opt-outs and reasons will be recorded. In collaboration with [name], the letter was designed for smokers with low health literacy based on established health communication principles. The written message is one page in length to minimize cognitive overload and burden and to maximize the effectiveness of the message.⁸⁶⁻⁸⁹ The estimated readability according to the Flesch–Kincaid Grade Level rating is 4.8 (5th grade). The letter will be printed on NNHSC letterhead, enclosed in large-sized (6" x 9") NNHSC envelopes, and sent first-class mail.

One day after letter mailing, the first automated text message will be sent to participants notifying them that they will receive the CtC letter in coming days. During the 10 days following the letter mailing, participants will receive three more automated text messages on behalf of their healthcare provider three days apart between each message. A fifth text message will be sent 8-10 days after the Quitline's initial outreach call (i.e., Quitline outreach takes place two weeks after letter mailing). The purpose of this last text message is to provide the toll free Quitline number in case the participant has not yet been able to connect with a Quitline counselor. Also informed by SDT and patient feedback, the automated text messages will be used to sustain the motivational effects of the letter and maximize the likelihood that participants will engage in and utilize Quitline treatment. Participants who do not want to receive these messages will be able to opt-out after each message. The automated text messaging procedures were established in our prior work (P01 HS021141; [name]).⁸¹ Text messaging is increasingly used in primary care to support processes of care and improve health

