PROTOCOL SHORT TITLE: Choose to Change – Reducing Tobacco Disparities

[figure not shown]
outcomes.⁹⁹ Text messaging improves attendance at healthcare visits,^{100,101} adherence to diabetes self-care¹⁰² and weight management regimens,¹⁰³ as well as the effectiveness of smoking cessation treatment.⁹⁹ Popularity of text messaging is high across racial/ethnic groups, socioeconomic levels, and ages.¹⁰²

Two weeks after letter mailing, participants will be contacted by a Quitline counselor and offered free person-centered behavior counseling (cessation or reduction-focused depending upon patient preference) and free NRT (patch, gum, or lozenge) if determined as safe and appropriate. Please see more detail regarding the proactive Quitline treatment below.

Usual Care Condition: Participants assigned to this clinic-based control comparison will receive NNHSC clinic-based care for smoking that follows the Ask, Advise, Refer approach.¹⁹ Following the practice adopted by NNHSC in 2011, a Usual Care participant who smokes will receive a referral for proactive Quitline treatment according to the following established clinic procedure: If the participant is seen in the clinic for a health problem or routine evaluation, a medical assistant will confirm current smoking and advise the participant to quit using clear and strong language. Current smoking and advice to quit are documented in the EHR system and the participant will be seen by the provider who addresses the purpose of the visit. If the provider also addresses the participant's smoking, establishes that the participant is motivated to set a quit date, and the participant agrees to the Quitline referral, a referral form is generated via the EHR system. Referrals are transmitted electronically via the Quitline website by the Care Coordinator. Participants who are referred will receive a call from the Quitline within 48 hours. Usual Care participants who accept Quitline treatment will receive free person-centered smoking cessation counseling and free NRT (patch, gum, or lozenge). Please note: providers may still refer patients who are not enrolled in this study to the Quitline.

In both conditions, Quitline treatment will continue as accepted or initiated by participants over 28 weeks.

Figure 3. Choose to Change Intervention Workflow

Choose to Change Intervention Clinic Workflow

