Treatment engagement will be measured at 6, 14, and 28 (as applicable) weeks after letter mailing, and operationalized as the proportion of participants who accept the proactive Quitline call and accept treatment as defined by completing the counseling session. Participants who return a Quitline call and accept treatment also will be counted as having engaged in treatment. Further, we will assess: 1) the proportion of smokers who request cessation versus reduction counseling; and 2) the proportion of smokers who engage in treatment and who request NRT and (or) schedule a follow-up (proactive or reactive) counseling call.

Treatment utilization will be measured at 6, 14, and 28 (as applicable) weeks and will be defined as the proportion of participants who complete ≥ 1 additional counseling calls and receive and use NRT. The frequency and duration of sessions will also be measured.

Smoking cessation at 6 and 14 weeks will be defined as self-reported abstinence (not even a puff of a cigarette) for ≥ 7 days. At 28 weeks, breath CO will be used to verify abstinence for participants in the original study timeline. For participants in the alternative shorter study timeline, breath CO will be measured at 14 weeks to verify abstinence. Participants will be classified as abstinent if they report not smoking (not even a puff of a cigarette) for ≥ 7 days and have a CO ≤ 8 parts per million (ppm). Participants will be assumed to be smoking if they report smoking, cannot be reached to provide data, fail to provide a breath sample, or provide a breath sample that is >8 ppm.¹⁰⁵ Participants who report abstinence at 28 weeks (original timeline) or 14 weeks (alternative shorter timeline) will be invited for an in-person visit for breath carbon monoxide (CO) measurement to bio-verify abstinence status.

Moderators, Mediators, and Covariates

Hypothesized moderators of Choose to Change effects will be measured at baseline and include readiness to quit smoking,^{96,97} recent smoking reduction,⁵¹ cigarettes per day, time since last clinic visit during which smoking was addressed, initial choice of cessation versus reduction, race/ethnicity, perceived stress, , and discrimination. Hypothesized mediators of intervention effects on treatment engagement, utilization, and cessation will be measured at each survey time point and will include perceived autonomy support, autonomous motivation, confidence in ability to quit, and attitude towards NRT.

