PROTOCOL SHORT TITLE: Choose to Change – Reducing Tobacco Disparities

- 8) Sending seasonal newsletters about living a healthy lifestyle;
- 9) Demonstrating a positive and caring attitude towards participants¹⁰⁹;
- 10) Rapid rescheduling of missed appointments; and
- 11) Acknowledgement and appreciation of participant effort.

These enrollment and retention strategies have been effective in pragmatic clinical trials and community studies of underserved populations,¹¹²⁻¹¹⁵ as well as in our ongoing cohort study (N01 HC48049).

STATISTICAL ANALYSIS PLAN

Power

To address power for hypotheses related to **Aim 1 (Treatment Engagement at 6 Weeks)**, we base our estimates for the proportion of participants completing a Quitline session by 6 weeks in the Choose to Change condition on our pilot study that resulted in a **24%** engagement rate. As for the Usual Care condition, we expect that current NNHSC Ask, Advise, Refer practice involving the Quitline as the primary referral program will result in a tripling to **10%** of the 3.3% engagement rate achieved in our EHR fax-referral project, in which our NIH-funded study of long-term nicotine patch treatment, with inclusion and exclusion criteria, served as the primary referral program.⁹⁴ Assumed rates by condition for each of the three outcomes of interest and participants per condition are presented in Table 3. We propose that a minimum of N=265 independent participants be randomized to Choose to Change versus N=265 to Usual Care, for a total N=530. Such a 1:1 allocation ratio guarantees **99% power** for the comparison of Choose to Change versus Usual Care at two-sided alpha=.05. This sample size requirement equates to 40 participants per month over the 15-month randomization period. In our three-week pilot study, 132 patients were processed through the workflow in Figure 3, a rate of 175 per month.

Table 3. Assumed Intent-to-Treat Rates by Condition for the Three Outcomes of Interest and Participants per Condition

Study Aim	Usual Care	Choose to Change
Aim 1: Engagement (6 Weeks)	10%	24%
Aim 2: Utilization (12 Weeks)	7%	15%
Aim 3: Cessation (26 Weeks)	2%	7%
Participants	265	265

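### The operational definition of engagement requires a prior outbound Quitline call, which is the default in one arm and conditional in the other, and it conflicts with the route-neutral wording of Aim 1

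*Combined protocol and SAP*

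**What the plan says.** Treatment Outcomes (under Measures) gives the only operational definition of engagement: "operationalized as the proportion of participants who accept the proactive Quitline call and accept treatment as defined by completing the counseling session". It then adds a second route: "Participants who return a Quitline call and accept treatment also will be counted as having engaged in treatment".

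The arms reach an outbound call differently.

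- **Choose to Change.** Under Choose to Change Intervention Clinic Workflow, contact details go to the Quitline after a 12-day opt-out period and participants are called within two days of referral. A fifth text follows 8 to 10 days after the initial outreach call: "The purpose of this last text message is to provide the toll free Quitline number".
- **Usual Care.** Under Usual Care Condition, a call follows only if the participant attends clinic, the provider addresses smoking and establishes motivation to set a quit date, and "the participant agrees to the Quitline referral, a referral form is generated via the EHR system".

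Two other places word the same outcome without regard to who placed the call. The Aim 1 hypothesis reads "Choose to Change will increase the proportion of smokers who complete a behavior counseling call by 6 weeks (24%), compared with Usual Care (10"%). The Power section likewise speaks of participants completing a Quitline session by 6 weeks.

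**The concern.** The definition ties a primary outcome to an event, an outbound call, that the intervention itself delivers. The same behaviour, dialling the Quitline and completing a session, can then be scored differently by arm. In Choose to Change, an inbound call made after outreach, perhaps prompted by the fifth text, fits the wording about returning a call. An unreferred Usual Care participant has no call to accept or return.

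Any session lost this way is lost mainly from Usual Care, so the Aim 1 difference would be overstated in favour of the intervention. The protocol also foresees such sessions: the end of the Usual Care section says that Quitline treatment in both conditions may be accepted or initiated by participants.

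**Working it through.** **1. The plan's own figure.** Inputs from Power: "N=265 independent participants be randomized to Choose to Change versus N=265 to Usual Care, for a total N=530"; rates of 10% and 24%; and "1:1 allocation ratio guarantees 99% power for the comparison" at two-sided alpha 0.05. With a pooled normal approximation, power = Φ[(d − 1.96·s0)/s1], where

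- d = 0.24 − 0.10 = 0.14, and the mean rate is 0.17
- s0 = √(2 × 0.17 × 0.83 / 265) = 0.0326
- s1 = √(0.10 × 0.90/265 + 0.24 × 0.76/265) = 0.0321
- (0.14 − 1.96 × 0.0326)/0.0321 = 2.37, so power = 99.1%

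Unpooled and continuity-corrected versions give 99.2% and 98.8%. The stated 99% reproduces, so the point concerns the definition and not the arithmetic.

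**2. The definitions side by side.** Consider a session completed within 6 weeks.

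| Who calls | Treatment Outcomes, read literally | Aim 1 and Power |
|---|---|---|
| Either arm, accepts or returns an outbound call | counted | counted |
| Choose to Change, dials in after outreach | can be counted as returning a call | counted |
| Choose to Change, dials in before outreach or after opting out | not counted | counted |
| Usual Care, dials in without referral | not counted | counted |

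The third row shows that the exclusion is not confined to Usual Care. It bears mainly on that arm, because most of its participants may never receive an outbound call.

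**3. Illustration of size.** The documents give no rate of unreferred Usual Care calls, so x below is an assumption. Suppose both arms truly complete sessions at 10%, nothing is lost in Choose to Change, and x points go uncounted in Usual Care. The observed Usual Care rate is then 10% − x, and the two-sided rejection probability is Φ[(x − 1.96·s0)/s1] + Φ[(−x − 1.96·s0)/s1], with s0 and s1 computed as in step 1 at the observed rates.

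For x = 2 points, s0 and s1 are both about 0.0249. The first term is Φ(−1.156) = 0.1238 and the second is Φ(−2.766) = 0.0028, which sum to 12.7%.

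| x uncounted (points) | Participants of 265 | False-positive rate, true rate 10% | False-positive rate, true rate 24% |
|---|---|---|---|
| 0 | 0 | 5.0% | 5.0% |
| 1 | 2.65 | 6.8% | 5.9% |
| 2 | 5.3 | 12.7% | 8.5% |
| 3 | 7.95 | 23.6% | 13.1% |

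The last column repeats the calculation at a common true rate of 24%, where the same x matters less.

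**The case against.** The strongest reply is that the exclusion is not settled. Aim 1 and Power would both count the unreferred caller. Multiple Sites says the Quitline will report outcomes for all participants who complete sessions, the Health Behaviors Assessment asks everyone about Quitline treatment, and Data Collection and Management plans to merge survey, EHR and Quitline data. This stands in part: the plan contains two unreconciled definitions, and a sensible analyst might apply the broader one. It does not remove the problem. The narrower wording is the operational one, and nothing says that Aim 1 overrides it. Nor does the plan say how an unreferred caller is recognised as a trial participant. The Clinic Workflow section mentions a Usual Care tracking code but is silent on how such a caller would get it. The survey item is not named as a source for this outcome, survey participation is expected to be at least 60%, and missing counts as failure.

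A second reply is that unprompted calls may be rare. Consent does not disclose the Quitline component, and the protocol describes 95% of smokers as not ready to attempt quitting. That is fair, and it is why no size is claimed.

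A reader might also infer that every Choose to Change participant has a call to accept or return. The documents do not support this: participants may opt out through the care coordinator or by text, outreach ends after three unanswered calls, and a message is left only on the participant's own voicemail.

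A reader might further carry the bias over to Aim 2. The utilization definition contains no proactive-call condition, and the same section recognises reactive follow-up calls, so no figure for Aim 2 is supported.

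**Conclusion.** The point holds as an unreconciled definition of a primary outcome, one version of which depends on treatment arm. Applied as written under Treatment Outcomes, it would favour Choose to Change.

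The size is unknown. The false-positive rates of about 7%, 13% and 24% rest on assumed losses of 1, 2 and 3 points in Usual Care only, a common true rate of 10%, no losses in Choose to Change, and an unadjusted comparison of proportions. They show that small differential losses matter, not that they will occur.

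It would be wrong to conclude that part of the planned 14-point difference is artefact. The Power section describes the outcome as completing a Quitline session, so the planned 10% may already include self-initiated sessions. Nor is the 99% power in error.

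**What to change.** Under Treatment Outcomes, define engagement in both arms as any completed Quitline counseling session by week 6 after week 0, whoever placed the call. Anchoring to week 0 also gives Usual Care a clear starting point, since the present text counts weeks from a letter mailing that this arm does not receive.

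Ascertain the outcome identically in both arms from the Quitline outcome reports already sent to the NNHSC EHR, irrespective of referral code, and state how a session by an unreferred caller is linked to the trial record. Name the survey's Quitline-treatment item, asked in both arms, as a sensitivity source for unreferred callers.

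The fix should not rest on sending the Quitline a list of all randomised participants. That could disclose people who never agreed to referral or who opted out of it. Verbal consent covers the survey only, and the privacy section describes the business associate agreement in terms of referral transmissions.

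The cost is wording and a specified use of data already collected. The Usual Care rate may be slightly higher, and self-report adds some error. If the planned 10% excludes self-initiated sessions and counting them adds 1, 2 or 3 points, the step 1 formula gives power against 24% of 97.8%, 95.1% or 90.6%, which is still ample.

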Participants in both treatment conditions will have the opportunity to receive the same proactive Quitline treatment consisting of person-centered behavior counseling and NRT. The Quitline protocol relies on treatment determined to be effective in the 2008 U.S. PHS Clinical Practice Guideline.⁵ Participants who are reached and who accept treatment will first be asked for basic sociodemographic and smoking information. After registration and brief assessment, either smoking cessation- or reduction- focused treatment will be delivered depending on patient preference. Participants who choose reduction as their initial treatment goal will be guided toward setting a quit date aided by NRT. For all participants who engage in treatment, a self-help packet (Quit-Kit) will be mailed to provide written information on the topics covered during the initial phone session. Most calls last about 30 minutes, with the behavior counseling portion lasting about 15 minutes. A free 8-week course of NRT (patch, gum, or lozenge) will be mailed in two week allotments to participants who are willing to set a quit date and interested in and eligible to use NRT (i.e., free of medical contraindication). Per Quitline policy for Chicago residents, NRT is offered at no cost for uninsured residents and reduced cost for those who have Medicaid insurance. Because free NRT increases use of quitline treatment,^{46,104} NRT will be made available at no cost to all participants to eliminate differential cost by insurance type as a potential confounder of intervention effects.

If a participant is reached by the Quitline counselor but has not received the Choose to Change letter, smoking cessation or reduction treatment will be offered and delivered according to the participant's preference. For participants not reached during the first call attempt, the Quitline counselor will make two more calls in the following two days. A voice message will only be left if the voicemail inbox belongs to the referred participant. If three calls are made without a response, the outreach process will end. The Quitline counselor will either call at times designated by the participant to be convenient or at varying times during the day. The Quitline provides services seven days per week, from 7:00 AM through 11:00 PM.

MEASURES

EHR Characterization of Population

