Our power estimates for **Aim 2 (Treatment Utilization at 14 Weeks)** will be based on Williams et al.⁹ who reported a 30% utilization rate for combined counseling and medication at a later time point than ours (6 months), following a face-to-face SDT-based intervention. Assuming 6-month utilization rates (one or more counseling calls after the initial counseling call) for the Usual Care and Choose to Change conditions of **7%** and **15%**, respectively, would be consistent with their treatment utilization odds ratio of 2.38 (95% CI=1.67-3.39), albeit at a lower baseline rate than they report. Our proposed randomization plan guarantees **84% power** for the comparison of Usual Care versus Choose to Change at two-sided alpha=.05.

Our power estimates for **Aim 3 (Smoking Cessation at 28 Weeks)** will be based primarily on Rigotti et al.²⁷ who reported 7-day point-prevalence abstinence rates at 14 weeks of 1% for standard care and 5% for population mail outreach under an Intent-to-Treat (ITT) approach. We expect that these 12-week ITT rates will rise to 3% in our Usual Care condition and 10% in the Choose to Change condition. Even if these rates then drop to **2%** in our Usual Care and **7%** in Choose to Change at 26 weeks, we still have **80% power** for the comparison of Choose to Change versus Usual Care at two-sided alpha=0.05.

Data Analysis

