All outcomes of interest for **Primary Aims 1-3** are binary (treatment engagement, treatment utilization, smoking cessation) and can be analyzed using logistic regression methods. Analyses will be conducted first using an ITT principle (missing=treatment failures). We will also conduct an adherence sample analysis that includes only participants reached at the 28-week follow-up ($\geq 75\%$ of the sample based on our experience). This approach addresses the question of effectiveness more directly, but it is subject to more bias if attrition is large or differential by treatment condition. Therefore, we will complement it by analysis of non-response patterns using sociodemographic (age, gender, race, ethnicity, marital status, household income, education), and healthcare (time since last clinic visit, type of health insurance) characteristics. These can be used to create propensity scores that allow for inverse-probability-weighting (IPW) of observed outcomes^{116,117} to achieve balance across potential confounders of the treatment-to-outcome relationship. Ideally, the distribution of propensity scores will show large overlap across study conditions. If not, that will be taken as evidence that completers are not comparable on measured confounders across conditions, and that one should refrain from

PROTOCOL SHORT TITLE: Choose to Change – Reducing Tobacco Disparities

further comparisons. PROC GENMOD of SAS/STAT 9.2¹¹⁸ can handle subject-level probability weights. Similar findings across all three approaches would increase confidence in the results overall. Both raw and adjusted rates will be presented for each outcome by study condition. For the cessation outcome, we will also explore the impact of smoking history (e.g., past year quit attempts, past referral for Quitline treatment), race, and gender on non-response. We will also use propensity score modeling to examine the relationship between treatment utilization at 14 weeks and abstinence at 28 weeks. Since available data indicate little effect of NRT type on outcome, we will model NRT dose/duration, while controlling for patterns of utilization.

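### Primary Aim 2 has two conflicting definitions of treatment utilization, and the planned rates and 84% power belong to only one of them

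*Combined protocol and SAP*

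**What the plan says.** Four places in the combined protocol and SAP bear on the event.

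- **Purpose of Study & Objectives, Primary Aim 2:** the hypothesised effect is to "increase the proportion of smokers who complete ≥ 1 additional behavior counseling calls by 14 weeks (15%), compared with Usual Care (7", the last figure also being a percentage. The event is a counseling call. NRT is not mentioned.
- **Statistical Analysis Plan, Power (Aim 2):** the parenthesis explaining the rates is again call-only, "one or more counseling calls after the initial counseling call". The 7% and 15% are attached to that event, with 84% power.
- **Measures, Treatment Outcomes:** utilization is "defined as the proportion of participants who complete ≥ 1 additional counseling calls and receive and use NRT". This is one proportion with joined conditions.
- **Data Analysis:** the primary outcomes "are binary (treatment engagement, treatment utilization, smoking cessation) and can be analyzed using logistic regression methods". Utilization is named but not defined.

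The time point varies as well. Primary Aim 2 and the power section's label for Aim 2 say 14 weeks. Table 3 says "Aim 2: Utilization (12 Weeks"). The power text says "Assuming 6-month utilization rates". Measures lists weeks 6, 14 and 28 without marking one as primary.

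**The concern.** A participant who completes a second call and never uses NRT is a success under the hypothesis and the power section, and a failure under Measures. Both texts are current, and nothing says which governs. An analyst would normally program the endpoint from Measures, and would then test a stricter event than the one hypothesised and powered. Without a rule, the definition can also be settled once both results are known.

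The choice may not affect the two arms alike. Choose to Change encourages reduction as a first goal. The section on proactive Quitline treatment says NRT is mailed to "participants who are willing to set a quit date and interested in and eligible to use NRT". If fewer Choose to Change repeat callers met that condition, the NRT requirement would remove proportionally more successes from that arm. This is plausible but not established, because the documents describe NRT supply in different ways. The intervention description and the clinic workflow do not state the quit-date condition. Potential Study Risks omits it too and instead ties supply to completing weekly counseling calls.

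**Working it through.** **Inputs.** From the power section and Table 3: 265 per arm, 1:1 allocation, two-sided alpha 0.05, Usual Care (UC) 7%, Choose to Change (CtC) 15%, stated power 84%.

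**Formula** (two-proportion test, pooled variance under the null, with p̄ the mean of p1 and p2):

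power = Φ{ [ |p2 − p1| − 1.96·√(2p̄(1 − p̄)/n) ] / √([p1(1 − p1) + p2(1 − p2)]/n) }

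**Step 1: reproduce the plan's figure.** p̄ = 0.11.

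- Null standard error: √(2 × 0.11 × 0.89/265) = 0.02718, and × 1.96 = 0.05328.
- Alternative standard error: √((0.0651 + 0.1275)/265) = 0.02696.
- (0.08 − 0.05328)/0.02696 = 0.991, and Φ(0.991) = **83.9%**.

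The 84% is right for the call-only event.

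**Step 2: does the cited odds ratio identify the definition?** The planned rates give (0.15/0.85)/(0.07/0.93) = 2.34, close to the cited 2.38. But the power section says its source "reported a 30% utilization rate for combined counseling and medication at a later time point than ours (6 months"). The effect size comes from a combined outcome and is applied to a call-only one, so it does not settle which event is meant. It supplies no combined rate for this trial either.

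**Step 3: the combined event.** It is a subset of the call-only event, so neither arm's rate can be higher than 7% or 15%. Let each arm have a share of repeat callers who also receive and use NRT. The documents give no such share, so **every share below is an assumption**. The rates are 0.07 × UC share and 0.15 × CtC share.

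| UC share | CtC share | UC rate | CtC rate | Power at 265 per arm |
|---|---|---|---|---|
| 90% | 90% | 6.3% | 13.5% | 79% |
| 80% | 80% | 5.6% | 12.0% | 74% |
| 60% | 60% | 4.2% | 9.0% | 61% |
| 50% | 50% | 3.5% | 7.5% | 52% |
| 90% | 80% | 6.3% | 12.0% | 62% |
| 90% | 70% | 6.3% | 10.5% | 41% |
| 70% | 80% | 4.9% | 12.0% | 84% |
| 80% | 90% | 5.6% | 13.5% | 87% |
| 60% | 80% | 4.2% | 12.0% | 91% |

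With equal shares of 90%, 80%, 60% and 50%, 84% power would need 299, 341, 466 and 566 per arm.

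**Step 4: break-even.** Solving for the CtC share that keeps 83.9% gives 93.5%, 86.9%, 80.1%, 73.1% and 65.9% for UC shares of 90%, 80%, 70%, 60% and 50%. The CtC share must exceed the UC share by about 4 to 16 points.

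**Step 5: measurement.** Completed calls reach the clinic record from the Quitline. No source is named for NRT use. If it came from the telephone surveys, where the retention section expects at least 60% participation, the missing-equals-failure rule would turn survey non-response into endpoint failure.

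**The case against.** The strongest reply is that the intended definition is clear enough. The hypothesis and the power section set the aim and the sample size, and both are call-only. The Data Analysis section also plans to model NRT dose and duration while controlling for utilization patterns, which treats NRT as something apart from utilization. On this view one Measures sentence is loosely worded, and a departure from the stated aim would be visible. This is good support for choosing the call-only definition. It does not remove the conflict, because no text gives the aim precedence over Measures.

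A second reply is that the power figures for the combined event rest on invented shares and fall on both sides of 84%. That is correct. They show that the result depends on an unstated quantity, not that power is lost.

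Third, the differences in NRT supply are partly explained. The intervention description refers the reader to the detailed Quitline section, the workflow text does not claim to list every condition, and participants who start with reduction are guided toward a quit date aided by NRT. This weakens the case for a lower CtC share. The clearest remaining discrepancy is between the Quitline section and Potential Study Risks.

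Fourth, the 12-week label may be a table-wide slip, since Table 3 also shows 26 weeks for Aim 3, where the aim says 28. The 6-month wording may be carried over from the cited study. Both explanations are likely, but the time point is part of the endpoint definition and still needs correcting.

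**Conclusion.** The concern holds: the plan is wrong as written. One of the three primary outcomes has two incompatible definitions in current text and no rule choosing between them. The 84% power is correct for at least one additional counseling call (83.9% recomputed) and for that event only. For the call-plus-NRT event the plan states neither rates nor power. Under assumed NRT shares, power ranged from 41% to 91%. It falls below the planned level unless the Choose to Change share is higher by roughly 4 to 16 points, for Usual Care shares between 90% and 50%. The definitional conflict rests on the text alone and needs none of these assumptions. It should be resolved before outcome data are analysed.

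**What to change.** **Preferred route.**

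- In Measures, define primary utilization as at least one additional completed counseling call by 14 weeks, taken from Quitline/EHR records.
- Report NRT receipt and NRT use as separate secondary measures.
- Name the same definition in Data Analysis.

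**If the combined event is kept.** State it in Primary Aim 2, Measures, Power and Data Analysis. Give assumed rates per arm, name the data source for NRT use, and restate the power.

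**Either way.**

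- Use one time point throughout, correcting the 12-week label in Table 3 and the 6-month wording in the power section. Week 14 is the last follow-up shared by the original and shortened timelines.
- Reconcile the statements on who is sent NRT in the intervention description, the clinic workflow, the proactive Quitline section and Potential Study Risks. Which condition applies is for the investigators to settle.

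**Cost.** The preferred route needs wording edits in Measures, Table 3, Power and Data Analysis, with no new data and no change from 265 per arm, and the 84% stands. The alternative needs planning rates that the documents do not contain and, depending on those rates, possibly a larger sample.
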